4.5.1 Initial Data Collection

Following the implant procedure (time zero), the following data will be collected and entered on the eCRFs while the pump is implanted:

- Two (2) hours post implant:
 - Vital signs (HR, BP, RR)
 - Fluid Ins and Outs since last reading
 - Hemodynamics
 - CVP
 - PA Systolic
 - PA Diastolic
 - PA Mean
 - PCWP
 - SvO2 as measured by the PA catheter
 - SaO2 as measured by pulse oximetry
 - Document any medication changes and adverse events
 - Urine labs per Appendix A
- Six (6) hours post implant and every 6 hours for 24 hours post implant:
 - Vital signs (HR, BP, RR)
 - Fluid Ins and Outs since last reading
 - Hemodynamics
 - CVP
 - PA Systolic
 - PA Diastolic
 - PA Mean
 - SvO2 as measured by the PA catheter
 - SaO2 as measured by pulse oximetry
 - Document any medication changes and adverse events
- Twelve (12) hours post implant and every 12 hours until Pump retrieval:
 - Blood and urine labs per Appendix A
- Twenty-four (24) hours post implant and every 24 hours until Pump retrieval:
 - Cardiovascular exam (edema, pulmonary auscultation, weight)
 - Vital signs (HR, BP, RR)
 - Fluid Ins and Outs since last reading
 - Hemodynamics
 - CVP
 - PCWP
 - PA Systolic
 - PA Diastolic
 - PA Mean
 - SvO2 as measured by the PA catheter
 - SaO2 as measured by pulse oximetry

- Dyspnea evaluation
- Document any medication changes and adverse events
- Blood labs per Appendix A

BMI will be calculated by the sponsor. Patient should be maintained on anticoagulation and antiplatelet therapy per **Appendix B**.

If the Aortix Pump is suspected to be malfunctioning or mal-positioned, imaging studies, diagnostic procedures, or access site exam may be performed as needed.

Prior to any unplanned retrieval of the Aortix Pump, hemodynamic and laboratory assessments should be repeated, and a fluoroscopic image of the pump position should be taken, and the image documented.

Refer to **Appendix A** for a detailed study monitoring schedule.

4.5.2 Programming the Aortix Pump/Pump Speed Changes:

4.5.2.1 Programming the Pump

The Aortix Pump should initially be operated at a speed of 25 krpm for a minimum of two days. The pump may be stopped once congestion and hemodynamic targets have been achieved for that patient as assessed by the investigator. The pump should be left in place for a sufficient time to achieve the diuresis and hemodynamic goals for the patient. All adjustments are at the discretion of the investigator according to their clinical judgement. Once congestion and hemodynamic targets have been achieved, diuretic or other therapies may be down titrated or discontinued, at the physician's discretion, but the pump should be kept running at 25 krpm. **If a decision is made to reduce the Pump speed, vital signs, hemodynamic measurements and fluid ins and outs must be recorded before speed reduction in accordance with Appendix A.**

If congestion and hemodynamic targets have not been achieved after 2 days, the pump speed may be turned up in 1 krpm increments to see if running the pump at a higher speed will provide benefit to the patient.

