After signing informed consent, a urinary collection device will be placed, if not already present. A Foley catheter is recommended, but an external urine collection device may be used per institution requirements. The urine collection device will be placed (do not measure the urine collected during catheter placement) at least twelve (12 hours) before the Aortix Pump placement. If a urinary collection device is already in place, urine should be discarded. Output and intake should be strictly observed starting twelve hours prior to the scheduled implant. The urine collection device and the strict ins/outs monitoring will continue until the Aortix pump is retrieved. The first measurement of intake and output should occur at least six hours prior to Aortix placement and should be recorded every two hours until the pump is turned on. Measurements will occur at the frequency outlined in **Appendix A**.

Fluid ins should be monitored (IV and Oral) for the entire duration the urine collection device is in place with final measurements taken at the time of device retrieval.

Patients will receive standard medical therapy throughout the study. Patients should be on optimized medical therapy prior to being considered for Aortix Pump placement. To characterize the effect of the experimental device, physicians should not adjust the diuretic or inotrope dosing regimen during the twelve (12) hours prior to or the twelve (12) hours after Aortix Pump placement, unless medically necessary. **Diuretics and inotropes should not be adjusted for twelve (12) hours after the Aortix pump is turned on, however, after that point, while the Aortix pump is running, cessation of medications or down titration of diuretics, inotropes or other medications are allowed.** Adjustments of medical therapy can otherwise be made at any point during the study period at the discretion of the treating physician. All medications and medications adjustments will be captured on eCRFs.

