4.5 Aortix Post-Deployment Monitoring and Management

The Aortix Pump has been tested to operate safely for 7 days of use. Aortix therapy should continue until objective signs of hemodynamic congestion have resolved, alternative / escalated therapy is required, or if device related safety concerns arise. The duration of Aortix pump use should be dictated by the physician's target for diuresis (net fluid and weight loss). In addition, the pre-specified target for pump effectiveness is a **minimum 20%** decrease in the patient's CVP and PCWP from pre-implant. **Diuretics and inotropes should not be adjusted for twelve (12) hours after the Aortix pump is turned on. After that point, while the Aortix pump is running, cessation of medications or down titration of diuretics, inotropes or other heart failure medications are allowed.** Adjustments of other medical therapy can otherwise be made at any point during the study period at the discretion of the treating physician. All medications and medications adjustments will be captured on eCRFs.

Refer to the Aortix System Instructions for Use (PPL004) for details of the Aortix Pump management.

If clinically significant device migration is suspected, use x-ray or another imaging modality to verify pump position.

It is recommended that the patient's vital signs be monitored frequently post procedurally (e.g., vitals checked every 15 minutes for the first hour, then every 30 minutes for the second hour). The patient's pedal pulses should be monitored post procedurally frequently for distal limb perfusion, ideally but not limited to, every fifteen (15) minutes times four (4), every thirty (30) minutes times two (2) and every hour (1) for two (2) hours and then as frequently as signs and symptoms warrant. In addition, the access site should be monitored for bleeding, hematoma, swelling or signs of infection.

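### The 12 h diuretic and inotrope freeze is meant to characterise the device effect, but no planned SAP summary or test isolates it, and the urine baseline uses only the last pre-implant interval

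*Protocol*

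**What the plan says.** **The freeze.** Protocol 4.3 gives the reason for it: "To characterize the effect of the experimental device, physicians should not adjust the diuretic or inotrope dosing regimen". It covers the 12 h before placement and the "twelve (12) hours after Aortix Pump placement, unless medically necessary". After hour 12 on the pump, section 4.5 says that "cessation of medications or down titration of diuretics, inotropes or other heart failure medications are allowed".

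**Data collected inside it.** Before implant: "Output and intake should be strictly observed starting twelve hours prior to the scheduled implant". The first intake and output measurement is due at least 6 h before placement, and fluids "should be recorded every two hours until the pump is turned on". On the pump, section 4.5.1 and Appendix A schedule CVP and fluids at hours 2, 6 and 12, PCWP at hour 2, BNP or NT-pro-BNP at hour 12, and urine labs at hours 2 and 12.

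**Timing of the endpoint reading.** Section 4.5.2.1: "The Aortix Pump should initially be operated at a speed of 25 krpm for a minimum of two days". Section 4.5.3 and Appendix A (footnote α) place the Congestion Target Met or therapy-ineffective assessments before weaning, no more than 12 h before it begins.

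**What the SAP reports.**
- 7.8.3: responder percentages and Wilcoxon tests on pressures and BNP, pre-implant against Congestion Target Met.
- 7.9.5: pressure summaries at Baseline and Congestion Target Met. Boxplots add Retrieval.
- 7.9.2: laboratory tables at Day of Implant, Congestion Target Met, 72 h or discharge, and follow-up.
- 7.8.3.1: an on-therapy urine rate from baseline to the final reading before retrieval (substitution disclosed in 7.14), against a baseline rate over the single interval that ends at the baseline reading.
- 7.8.3.1, 7.9.2 and 7.9.5: per-patient plots that do include hours 0–12.

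**The concern.** The study has no control arm. Hours 0–12 on the pump, set against the frozen hours before implant, form the one before-after contrast in which diuretic and inotrope doses are held by protocol. Sites and patients bear that restriction for a stated analytic purpose, yet the SAP names no group result that serves it. The planned endpoints answer a different question: what happened over pump therapy together with whatever drug changes followed hour 12.

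Urine output has a second weakness. One interval of about 2 h is the comparator for two days or more on the pump. A short interval is noisy. If diuretic is given as boluses, it also depends on whether a dose happened to fall just before it.

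Section 7 of the protocol says the study is to inform the design of later studies. A pre-specified estimate with drug doses held would be useful there, and individual plots do not supply one.

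**Working it through.** The plan states no figure on this point, so there is none to reproduce. The check is timing arithmetic plus a comparison of scheduled data with planned outputs.

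**1. Earliest endpoint reading for a patient who completes the two-day minimum.**
- Inputs: 48 h at 25 krpm (4.5.2.1); reading at most 12 h before weaning (4.5.3); freeze ends at hour 12 (4.3, 4.5).
- Earliest reading = 48 − 12 = hour 36.
- Gap after the freeze = 36 − 12 = 24 h.

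**2. Share of frozen hours in the on-pump urine window.** Share = 12 / T, where T is hours from pump-on to the final reading before retrieval. Weaning takes ideally at least 2 h + 1 h = 3 h (4.5.4).

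| T (h) | Share |
|---|---|
| 36 (early retrieval) | 33.3% |
| 48 | 25.0% |
| 51 (48 + 3 h weaning) | 23.5% |
| 72 | 16.7% |
| 96 | 12.5% |
| 168 (7 days) | 7.1% |

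So hours 0–12 are used in the rate but diluted. The 25% ceiling applies only to patients who complete 48 h.

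**3. Urine baseline.** With readings every 2 h, the last interval is nominally 2 h.
- Share of the frozen pre-implant hours used: 2 / 12 = 16.7%.
- Share of the minimum recorded collection used: 2 / 6 = 33.3%.
- Comparison as planned: about 2 h against 48 h or more. Comparison available: 6 to 12 h against 12 h.

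**4. Scheduled readings against planned group results.**

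| In-window data | Group summary or test that isolates it |
|---|---|
| CVP at 2, 6, 12 h | None; listings and per-patient plots |
| BNP or NT-pro-BNP at 12 h | None; listings and per-patient plots |
| Urine output, hours 0–12 | None; pooled into the whole-therapy rate |
| Frozen pre-implant fluids | Last interval only |

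**5. Fit of the hour-12 readings to the freeze.** Appendix A allows ±1 h, so readings fall at 11 to 13 h and can lie at most 1 h outside it.

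**6. Drug-dose analyses.** SAP 7.4.2 and 7.4.3 compare the 48 h before treatment with the whole pump period. Of that 48 h, 12 / 48 = 25% is frozen. Neither analysis splits the pump period at hour 12.

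**The case against.** The strongest reply is that this is a pilot. Protocol section 7 says patients will be reviewed individually, and the plots do that for every reading in the window. The sample size was not statistically derived, no success criterion depends on hour 12, and medians could be computed later from the listings. That limits the seriousness. It does not remove the point, because the same section plans summary statistics and input to later designs, and the SAP already plans group tests. In an uncontrolled study, an early timepoint chosen after the data are seen carries less weight than one named beforehand.

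SAP 3.1 promises data at each scheduled timepoint where applicable. The specific sections name their timepoints and omit hours 2 to 12, so the general rule cannot be relied on to fill the gap.

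Hour 12 is not a pure device effect either. It follows an invasive procedure, patients are selected on raised pressures so regression to the mean remains, and PCWP is not scheduled then. All of that stands, and is why the readout should be labelled supportive.

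Two stronger readings are tempting, and the documents support neither.
- A reader might infer that the frozen-window data go unused. Urine output from hours 0–12 is part of the primary on-therapy rate, pre-implant readings serve as comparators, and SAP 7.4 tabulates diuretic and inotrope doses at Day of Implant and Congestion Target Met.
- A reader might infer that later drug changes flatter the device. What is expressly allowed after hour 12 is stopping or reducing doses, which would tend to work against it. The direction is not fixed, because 4.3 says "Adjustments of medical therapy can otherwise be made at any point during the study period at the discretion of the treating physician" while 4.5 says "Adjustments of other medical therapy can otherwise be made at any point during the study period at the discretion of the treating physician", and these differ on whether diuretics and inotropes may be increased.

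**Conclusion.** The point holds as a gap in the analysis plan that should be closed. It does not invalidate the endpoints: the pre-weaning reading remains a sound end-of-therapy measure.

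For patients who complete two days, the pressure and BNP endpoint reading comes at least 24 h after doses cease to be held. Frozen hours are then 25% of the on-pump urine window or less, falling to 7.1% at seven days. Two days is guidance subject to investigator judgement, and protocol 5.3 allows retrieval at any time, so patients retrieved early can have an earlier reading and a larger share (33.3% at 36 h). The urine baseline uses nominally 2 of 12 frozen hours.

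These figures assume readings at their nominal times and a urine window counted from pump-on. The contribution of later drug changes to the endpoints cannot be computed from the documents. Nor can the gain in precision from a longer urine baseline, because no variability data are given.

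**What to change.** 1. **SAP 7.8.3.1.** Compute the baseline urine rate over the whole frozen pre-implant collection (12 h where available, at least 6 h) instead of the last interval. Add the urine rate over hours 0–12 on the pump and its change from that baseline. Record the new definition in 7.14.
2. **SAP 7.8.3.** Add a supportive summary of change in CVP, and in BNP or NT-pro-BNP (each assay separately), from Day of Implant (Pre-implant) to hour 12. Flag patients whose diuretic or inotrope dose changed inside the freeze, and any reading in the ±1 h window taken after a dose change.
3. **Keep** the pre-weaning reading as the end-of-therapy endpoint.

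Do not add a table of responder status by dose change. Protocol 4.5.2.1 permits down-titration once targets are met, so a lower dose can be a result of response, and such a table would invite reverse causation.

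The cost is a few table rows and one changed derivation. No new visit, sample, catheter reading or eCRF field is needed, because hour-12 CVP, BNP and fluids, the 2-hourly pre-implant fluids and medication changes are already collected. The limits should be stated beside the table: no PCWP at hour 12, and no protection from regression to the mean or procedural effects.

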4.5.2.2 Monitoring Hemolysis and Adjusting Pump Speed

Careful monitoring for hemolysis should be coincident with adjusting the pump speed. Plasma free hemoglobin (pfH) (every 24 hours), LDH (every 12 hours) and urine hemoglobin^{xi} (every 12 hours) measurements should be taken while the pump is implanted to confirm there is no hemolysis. After every speed change (before the congestion target met/therapy deemed ineffective timepoint), pfH/LDH and urine hemoglobin measurements should be assessed before contemplating an additional speed change. As such, speed changes should only be made every 12 hours. Patients should be regularly monitored for signs of hemolysis (e.g. hemoglobinuria, cramping) as hemolysis may occur and not be recognized until the next pfH/LDH measurement. The maximum speed is 28k rpm.

Aortix Pump speed may be reduced to the last speed with no hemolysis if hemolysis or safety concerns arise.

^{xi} Only required if collected as part of routine standard of care urinalysis.

4.5.3 Congestion Target Met/Therapy Deemed Ineffective Data Collection

Once the congestion target has been met or therapy has been deemed ineffective, before weaning begins, the following assessments should be made within 12 hours of beginning weaning:

- Cardiovascular exam (edema, pulmonary auscultation, weight)
- Vital Signs (HR, BP, RR)
- Dyspnea evaluation
- Fluid Ins and Outs since last reading
- Hemodynamics:
 - CVP
 - PA Systolic
 - PA Diastolic
 - PA Mean
 - PCWP
 - SvO2 as measured by the PA catheter
 - SaO2 as measured by pulse oximeter
- Echocardiogram
- Blood and urine labs per Appendix A
- Document any medication changes and adverse events

If the congestion target timepoint overlaps with a scheduled assessment (e.g, an every 24 hour hemodynamic measurement), the scheduled assessment value can be used and also entered on the congestion target met timepoint eCRF.

4.5.4 Weaning the Pump Speed

Once the decision has been made to cease therapy, the pump speed may be adjusted down gradually (in increments of 2-5 krpm) while monitoring the patient's hemodynamics and urine output. The pump speed may be reduced to 18-20 krpm before it is retrieved. This process should ideally be conducted over a **minimum timeframe** of three hours with a minimum of two hours to reduce the speed to 18-20 krpm and a minimum of one hour of observation of the patient before removal. Only once in the cath lab and ready for retrieval should the Pump be turned OFF.

Figure 2 summarizes the pump programming steps.

[figure not shown]

Figure 2: Pump Programming

4.6 Day of Retrieval/Aortix Retrieval Procedure

4.6.1 Prior to Retrieval

The day of the Pump retrieval, before the Pump is retrieved, the following assessments should be made:

- Document any medication changes and adverse events

Before the Pump is retrieved, *in the cath lab*, the following assessments should be made:

- Vital Signs (heart rate, blood pressure, respiratory rate)
- Hemodynamics:
 - CVP
 - PA Systolic
 - PA Diastolic
 - PA Mean
 - PCWP
 - SvO₂ as measured by the PA catheter
 - SaO₂ as measured by pulse oximeter
- Fluid Ins and Outs since last reading
 - Fluid Ins and Outs should be recorded at the current pump speed per **Appendix A**.
- Blood labs per **Appendix A**.

After these measurements are taken, the Pump can be programmed to OFF and the retrieval procedure can commence.

4.6.2 Retrieval Procedure

A fluoroscopic image of the final pump position should be taken and documented before the pump is retrieved. The image should be sent to Procyrion.

Accessing the arteriotomy for Aortix Pump retrieval should be performed via a percutaneous technique or a cutdown, at the physician's discretion. Following pump retrieval with the Aortix Retrieval System, the arteriotomy should be closed using percutaneous or surgical techniques. Ultrasound or another technique should be used after retrieving the pump to verify the femoral artery is not occluded after closure (no vascular damage or clots). Careful post procedure assessment of peripheral pulses should follow the same protocol as the initial procedure. The retrieval site should be monitored for bleeding and hematoma. Prophylactic antibiotics according to standard of care are recommended.

Refer to Aortix System Instructions for Use (PPL004) for details of the Aortix Pump retrieval.

All Aortix Pumps and Aortix Control Systems should be returned to the sponsor using the supplied Aortix Return Kit. Any components of the Aortix Delivery System or Aortix Retrieval System that malfunction or are associated with an Adverse Event should also be returned to the sponsor using the supplied Aortix Return Kit.

4.7 Post Device Retrieval Monitoring

Following Aortix Pump retrieval, the patient will continue to receive routine standard of care for ADHF. After removal of the Aortix pump, the femoral artery should be monitored using hospital standard operating procedures for care of large bore arterial access procedure sites.

Following the retrieval procedure, the patient will be monitored until discharge as follows:

- Twenty-four (24) hours post retrieval and every 24 hours until discharge/seventy-two hour post retrieval timepoint:
 - Measure and record fluid ins and outs (if urine collection device still in place)
 - Blood labs per Appendix A
 - Document any medication changes and adverse events
- Once at seventy-two (72) hours (± 4 hours) post retrieval or at discharge (whichever is earlier):
 - NYHA classification
 - Cardiovascular exam (edema, pulmonary auscultation, weight)
 - Vital signs (HR, BP, RR)
 - Dyspnea evaluation
 - Blood and urine labs per Appendix A
 - Document any medication changes and adverse events

4.8 Follow-Up

Patients with the pump implanted will be followed for adverse events for 30 days (± 7 days) post device retrieval. If implanted patients are still hospitalized at 30 days due to an adverse event relating to the device or any study related procedures, they must be followed until resolution of the adverse event, resolution with sequelae, or until a terminal event. Protocol required data collection for patients with the pump implanted will be for 30 days post device retrieval (± 7 days) per **Appendix A**.

The following data will be collected:

- NYHA classification
- Cardiovascular exam (edema, pulmonary auscultation, weight),
- Vital signs (HR, BP, RR)
- Dyspnea evaluation
- KCCQ, EQ5D
- Document current cardiovascular/renal medications and adverse events
- Blood and urine labs per **Appendix A**

Patients that have an attempted implant but do not have the pump implanted will be followed for adverse events for 30 days (± 7 days) post attempted implant. If attempted implant patients are still hospitalized at 30 days due to an adverse event relating to the device or any study related procedures, they must be followed until resolution of the adverse event, resolution with sequelae, or until a terminal event.

Terminal events are death, LVAD implantation, heart and/or kidney transplantation, dialysis, ultrafiltration or CRRT.

Patients who are enrolled and undergo anatomy screening and/or invasive hemodynamic measurements who do not have an attempted implant will be followed for adverse events for 7 days (\pm 2 days) post anatomic screening or invasive hemodynamics (whichever is later) or until hospital discharge, whichever is first.

Every attempt should be made to perform follow-up visits in person. Should extenuating circumstances (e.g., COVID-19 global pandemic travel restrictions) impact a site's ability to perform follow-up visits in person, notify the sponsor and make every attempt to collect the protocol required data via other means (e.g., telephone, video conference, blood and urine labs at a non-hospital lab).

